7. STATISTICAL ANALYSES

Detailed statistical analyses is outlined in the statistical analysis plan (SAP). Briefly, the following analyses will be conducted.

7.1. Descriptive analyses

Descriptive statistics will be presented to describe patient characteristics such as age at transplant, sex, race/ethnicity, occupation, geographical location of residence, reasons for transplant, co-morbid conditions and immunosuppressive agents used in the voriconazole exposed and unexposed cohorts.

Counts and percentages to describe categorical variables, and mean and standard deviations (or median with inter quartile range (IQR), where appropriate) for continuous variables will be calculated.

7.2. Incidence estimates

Incidence rates of SCC of skin and melanoma by voriconazole exposed cohort and unexposed cohort will be calculated. Patients with a history of SCC will be excluded, when estimating the SCC incidence, and patients with a history of melanoma will be excluded when estimating the melanoma incidence.

The incidence estimates will be stratified by selected variables such as:

• Age at transplant

- Gender
- Race/ethnicity
- Occupation
- Skin phototype
- Geographical location
- Exposure to sunlight
- Reason for transplant
- Co-morbid conditions
- Immunosuppressive agents used
- Number of transplant rejection episodes
- Number of episodes of neutropenia after transplant

If there are sufficient number of patients with previous SCC in LT patients, incidence of recurrent SCC will be estimated among patients with history of SCC and the risk factors for recurrent SCC will be evaluated in univariate and multivariate analyses.

7.3. Univariate and multivariate analyses

The regression analyses will be performed separately for the study primary and secondary objectives.

7.3.1. Analyses to address primary objective

Comparison of voriconazole exposed cohort and unexposed cohort: A univariate Cox proportional hazard regression analysis will be conducted to assess the association between voriconazole and SCC of skin. Based on the results of the univariate analysis, a multivariate Cox proportional hazard regression model will be developed to evaluate the independent effect of voriconazole use on the risk of SCC of skin while controlling for effects of major confounding variables such as exposure to sunlight (using geographical location of residence as a proxy variable), immune status (using immunosuppressive medications as a proxy variable) and confounding by indication (using underlying medical conditions as a proxy variable). In addition to multivariate regression analyses, other analytic methods will be considered in order to control for major confounders such as patients' immune status and exposure to sunlight.

Further, depending on the number of patients, subgroup analyses such as comparison of patients who receive voriconazole but no other antifungals (i.e., 'voriconazole only cohort') with patients who did not receive voriconazole (i.e., unexposed cohort) will be considered to assess the association between voriconazole and SCC of skin.

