3.3. Definition of exposed and unexposed cohorts

Voriconazole exposed cohort: Patients with LT who receive at least one dose of voriconazole regardless whether they also receive other antifungals will be included in this cohort.

Unexposed cohort: Patients with LT who did not receive voriconazole will be included in this cohort.

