3.5. Index date and follow up

The index date will be the "date of LT". The study eligible patients will be followed from the index date to whichever of the following occurs first:

- Occurrence of SCC of skin or melanoma (follow up will be continued for the occurrence of a second endpoint if the patient develop one endpoint)
- Death
- Last patient visit or 31 December, 2012, at which time all surviving patients will be censored, whichever occurs first.

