3.9.1. Voriconazole and other antifungal treatment

Data on voriconazole therapy will include:

- Indication:
 - o Prophylaxis of IFIs
 - o Treatment of IFIs
- Dose and frequency
- Duration of therapy (will be calculated by using the treatment start and stop dates)

Data on antifungl agents other than voricoanzole (e.g., itraconazole, posaconazole, amphotericin B) will also be collected.

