7.3.2. Analysis to address secondary objective

In order to assess the potential association between voriconazole use and the development of melanoma, a similar analytic approach, described in section 7.3.1, will be used.

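### The optional 'voriconazole only' comparison defines its cohort by later antifungal use, so its hazard ratio can be biased in either direction; it should be defined on person-time instead

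*Protocol*

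**What the plan says.** Protocol section 3.3 places a patient in the exposed cohort after one dose of voriconazole, "regardless whether they also receive other antifungals will be included in this cohort". The unexposed cohort is everyone who did not receive voriconazole; other antifungals are allowed.

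Section 7.3.1 uses Cox regression for SCC and then adds an optional analysis: "depending on the number of patients, subgroup analyses such as comparison of patients" on voriconazole alone with the unexposed cohort will be considered. The comparison is a "comparison of patients who receive voriconazole but no other antifungals (i.e., 'voriconazole only cohort') with patients who did not receive voriconazole". No period is given over which the absence of other antifungals is judged. Section 7.3.2 carries this over to melanoma: "a similar analytic approach, described in section 7.3.1, will be used".

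Under section 3.5, follow-up runs from the transplant date to 31 December 2012 at the latest, and "follow up will be continued for the occurrence of a second endpoint if the patient develop one endpoint". Section 3.9.1 lists start and stop dates for voriconazole. For the rest it says only: "Data on antifungl agents other than voricoanzole (e.g., itraconazole, posaconazole, amphotericin B) will also be collected".

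**The concern.** Whether a patient belongs to the 'voriconazole only' cohort is known only after the antifungal record has been read forward from transplant, possibly for years. A Cox model that starts at transplant treats that membership as known on day one. Two readings are open, and they err in opposite directions.

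- **Antifungals started after SCC count.** A patient takes voriconazole alone, develops SCC and is then given another agent because of it. Follow-up continues for melanoma, so the later agent can be in the database. The patient is dropped although all exposure before the event was voriconazole alone, and the estimate falls.
- **Only antifungals started before SCC count.** A patient who stays event-free for longer has more time to receive a second agent and be dropped, together with that event-free time. A patient with early SCC stays in, and the estimate rises.

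This is the only exposure-refined comparison that 7.3.1 names, so readers of a safety study committed to the EMA may take it as the cleaner estimate of voriconazole's own effect. Section 8 does not list this bias among the limitations. It is distinct from immortal time before the first dose: the calculations below start voriconazole at transplant in every exposed patient, and the bias remains.

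**Working it through.** **1. The plan's own figure.** Section 3.8 and Appendix 1 give p0 = 0.05, RR = 2.5 (so p1 = 0.125), ratio 1:2, two-sided 5% and 80% power. The pooled proportion is (0.125 + 2 × 0.05)/3 = 0.075.

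n = [1.96·√(1.5 × 0.075 × 0.925) + 0.8416·√(0.125 × 0.875 + 0.05 × 0.95/2)]² / 0.075² = 156.9, so 157 exposed and 314 unexposed, as stated. This is for the main cohorts. No size is given for the subgroup.

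**2. Inputs for the bias.**
- From the protocol: transplants 2005–2008 and end of follow-up 31 December 2012, so 4 to 8 years of potential follow-up; unexposed SCC risk about 5%; true ratio 1.0 or 2.5.
- Assumed: unexposed SCC hazard λ0 = 0.0111 per year (4.8% cumulative after allowing for death); death hazard μ = 0.10 per year; administrative end C uniform on 4–8 years; voriconazole started at transplant; and the switching figures below. The protocol gives no switching rates.

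**3. Downward case.** A share q of exposed cases switch because of SCC and are removed. With D cases and PT person-years per exposed patient, of which PTc belong to cases, the ratio is D(1 − q)/(PT − q·PTc)/λ0.
- True 1.0: D = 0.04819, PT = 4.341, PTc = 0.131.
- True 2.5: D = 0.11519, PT = 4.151, PTc = 0.307.

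| q | true 1.0 | true 2.5 |
|---|---|---|
| 25% | 0.76 | 1.91 |
| 50% | 0.51 | 1.30 |
| 75% | 0.26 | 0.66 |

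A hand check on risks at the planned size: 157 × 0.125 = 19.6 exposed cases. Removing half leaves 9.8 of 147.2, or 6.7%. Against 5% that is a ratio of 1.33 in place of 2.5.

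**4. Upward case.** Switching is unrelated to SCC at rate s, and only switches before SCC or the end of follow-up count. Let a = λ + μ and b = a + s. Averaged over C, the retained patients supply
- events: D(s) = λ(1 − e^(−bC))/b
- person-years: PT(s) = a[1 − e^(−bC)(1 + bC)]/b² + C·e^(−bC)

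| s per year | D(s), true 1.0 | PT(s), true 1.0 | ratio, true 1.0 | ratio, true 2.5 |
|---|---|---|---|---|
| 0 | 0.04819 | 4.341 | 1.00 | 2.50 |
| 5% | 0.04224 | 3.319 | 1.15 | 2.86 |
| 10% | 0.03732 | 2.556 | 1.32 | 3.27 |
| 20% | 0.02980 | 1.552 | 1.73 | 4.26 |

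At 10% per year the rule removes 41% of the person-time but only 23% of the events: 0.774/0.589 = 1.31. Large Cox simulations (1.5 million patients) on similar assumptions gave 1.16, 1.32 and 1.73 for this case with a true 1.0, and about 0.75, 0.51 and 0.25 for the downward case.

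**5. Patterns with little or no bias.**
- If 20–40% switch, all within the first 6 to 12 months and none because of SCC, simulation with a true 1.0 gives 1.00 to 1.10.
- If ordinary switches count equally before and after SCC and none is triggered by it, the ratio is about 1.00.
- If unexposed patients start voriconazole later at the same yearly rate and are removed in the same way, both groups lose time alike. The step 4 formulas, applied to both, give 1.00 for a true 1.0 and 2.49, 2.48 and 2.46 for a true 2.5.

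**6. Censoring at the switch.** Person-time becomes (1 − e^(−bC))/b while events remain λ(1 − e^(−bC))/b, so the rate is exactly λ and the true ratio is recovered. Simulation gave 0.98–1.03 and 2.45–2.57. This holds when switching is independent of SCC risk.

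**The case against.** The strongest objection is that the protocol nowhere says 'never' or 'at any time'. Section 7 introduces its methods as brief and refers to an SAP that is not shown and could supply a window. That is fair as to what the SAP may contain. But the protocol does state a definition, and as worded it depends on the future.

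A reader might also infer more than the documents support:

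- **That the study's main result is compromised.** It is not. The main exposed cohort keeps patients whatever other antifungals they receive, so this rule removes nobody from it. The subgroup is one example of an analysis that will be considered if numbers allow.
- **That the distortion falls on the voriconazole group alone, with a known size and direction.** The unexposed cohort is itself defined by not receiving voriconazole later, and equal late starts cancel the upward bias (step 5). The two directions also come from mutually exclusive readings. The downward one is less natural, since follow-up for SCC ends at SCC, and it needs a sizeable share of cases to switch because of SCC, which no passage documents.
- **That switching is spread evenly over years.** Section 8 says most patients receive antifungals at the time of transplant. This lends some support to early use, where the bias is small.

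These points limit the size of the concern. They do not remove the dependence on later treatment.

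**Conclusion.** The concern holds for the optional subgroup only. If the 'voriconazole only' comparison is run as worded, for SCC or for melanoma, its hazard ratio can be biased either way. On the assumptions above, a true 1.0 could appear as about 0.25 to 0.75 (25–75% of exposed cases switched because of SCC, with those switches disqualifying) or about 1.15 to 1.7 (5–20% switching per year, counted only before SCC). The net size and direction are not established: they depend on switching rates and a counting rule that the protocol does not give, and benign patterns leave little or no bias. The change is worth making because it is cheap and the date field is best settled before abstraction.

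**What to change.** In section 7.3.1, and through it 7.3.2, define 'voriconazole only' as person-time that uses past information only:

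- Time from the first voriconazole dose counts while no other systemic antifungal has been received since transplant.
- At the first other antifungal, censor the patient from this comparison or move the patient to a time-varying 'voriconazole plus other' category.
- Treat the comparator the same way: patients contribute unexposed time until any first voriconazole dose.
- Ignore antifungals started on or after the date of the endpoint being analysed.
- Add start dates for the other antifungals to section 3.9.1.

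Censoring and the separate category leave the same 'voriconazole only' events and person-time, so neither corrects for switches prompted by early skin changes. For that, use inverse-probability-of-censoring weights, or lag the switch date so that events within a set period after the switch are attributed to 'voriconazole only'. Report the ever-exposed analysis alongside.

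The cost is a few sentences, slightly more programming and one added date field. Late events after a switch do not count in this subgroup; they stay in the main analysis.

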7.3.2. Analysis to address secondary objective

In order to assess the potential association between voriconazole use and the development of melanoma, a similar analytic approach, described in section 7.3.1, will be used.

8. STRENGTHS AND LIMITATIONS

Strengths:

- **Control for potential confounders:** This study will attempt to control for the confounding effect of patient immune status, which is a well known confounder, when assessing the potential association between voriconazole use and SCC of skin and melanoma among patients with LT. Multivariate Cox proportional hazard regression and other analytic methods, as appropriate, will be used to evaluate the independent effect of voriconazole use on the risk of SCC of skin while controlling for effects of confounders.
- Use of a retrospective cohort study design: A retrospective cohort study design will be used to address the research question. One of the major advantages of a retrospective cohort study over a case-control study is that the incidence of SCC of skin in LT patients receiving voriconazole can be estimated and compared with LT patients who did not receive voriconazole, and compare the characteristics of the two groups such as demographic variables, comorbid conditions, concomitant medication use, especially immunosuppressive agents. Further, in addition to the SCC of skin, other endpoints (e.g., melanoma) can be studied using a retrospective cohort study design.
- Use of real world data: This study evaluates the potential association between voriconazole use and SCC of skin and melanoma in patients with LT in a real-world setting using data from multiple transplant centers.
- **Generalizibility of findings**: This study will include patients with LT from several transplant centers in the EU, North America and Australia. Therefore, the results are likely to be generalizable to patients who underwent LT with regards to the risk of SCC of skin and melanoma.

Potential limitations:

- **Confounding by indication:** Confounding by indication is likely to take place in this study if a physician's decision to initiate a particular antifungal (s) for prophylaxis is influenced by the clinical status of the patient. This is of particular concern for voriconazole, which is a preferred antifungal agent in many transplant centers, as physicians are more likely to use voriconazole if patients are severely ill or are at high risk of acquiring IFIs. This could result in an association of voriconazole use with untoward outcomes including SCC of skin or melanoma. Although complete control of confounding by indication may not be possible, data on co-morbid conditions and laboratory tests will be collected and used in the statistical analyses (i.e., multivariate regression) for controlling its confounding effect.
- Generalizibility of study findings to voriconazole treated patients overall: It should be noted that the findings from such a study may not be generalizable to all voriconazole-treated patients with regards to the risk of SCC of skin as patients with LT are a special patient population with unique factors that make them more susceptible to SCC of skin.

- **Confounding by study center:** This study will include data from several transplant centers in the EU, North America and Australia. Therefore, factors such as sun exposure levels, and management and treatment of patients with LT will vary by study centers. The potential confounding effect by study center will be accounted for in the statistical analyses.
- **Misclassification of exposure:** The data on medication use more than three months prior to the transplant may not be available for most patients. which may result in misclassification of exposure. However, since the majority of patients receive antifungals at the time of transplant, the proportion of patients who may have received antifungal(s) three months before LT would be very small.
- **Exposure to sunlight:** Patients' exposure to sunlight has been identified as a risk factor for the SCC of skin. Exposure to sunlight or use of sun protective measures is not routinely documented in medical charts for all patients with LT. A proxy variable based on a patient's area of residence (e.g., highly exposed to sunlight versus not) will be developed and used in the analyses in the absence of individual-level data on exposure to sunlight.

9. ANTICIPATED STUDY TIMELINE

The estimated completion time of this retrospective cohort study is approximately two and a half years after the protocol endorsement. It will take approximately four months to recruit transplant centers including obtaining IRB/EC approvals, three months for development of the study database structure, 12 months for data collection/compilation, three months for data cleaning/verification, and nine months for statistical analyses and the study report development. The final study report is expected in the third quarter of 2015. The updates on the progress of the study will be provided to the EMA annually.

- Incidence of SCC of skin in LT patients unexposed to voriconazole (p₀) ranges from 3.0% to 15.0%. In order to estimate the sample size for a cohort study, it is necessary to specify the value of p₀, the rate of SCC of skin in patients unexposed to voriconazole, from the same source population (i.e., patients with LT) from which the voriconazole cohort will be drawn. The data on p₀ in the published literature is limited. Only one study was identified that reported an incidence of 9.9% for SCC and/or BCC of skin in patients with LT [16]. However, several published papers reported SCC of skin incidence in similar patient populations (i.e., renal, heart, or liver transplant patients) [19-22].³ For sample size calculations, it is reasonable to assume that the value of p₀ will range from 3.0% to 15.0%.

Table 1. Sample size estimations for a retrospective cohort study of LT patients with a range of p_0 , detectable RRs, and voriconazole exposed-to-unexposed cohort ratios, with 80% power at a 5% significance level

³ The incidence of SCC of skin in other organ transplant patients (i.e., other than lung or lung/heart transplant patients) is reported to range from 3.45% in patients with renal transplant patients in UK, 4.6% in patients with renal liver, heart, lung or pancreas transplant in Sweden, 12.6% in patients with liver transplant in the US, to 12.6% in patients with renal transplant in Spain.

p 0	RR to be detected	Minimum number of patients required in voriconazole exposed cohort and unexposed cohort for various exposed to unexposed ratios:						
	uttetteu	1:1		1:2		1:3		
		Voriconazole	Non	Voriconazole	Non	Voriconazole	Non	
		Cohort	Voriconazole	Cohort	Voriconazole	Cohort	Voriconazole	
			Cohort		Cohort		Cohort	
	2.0	749	749	536	1072	464	1392	
3.0	2.5	385	385	272	544	233	699	
	3.0	245	245	171	342	146	438	
	2.0	552	552	396	792	343	1029	
4.0	2.5	283	283	200	400	172	516	
	3.0	179	179	125	250	107	321	
	2.0	435	435	312	624	270	810	
5.0	2.5	222	222	157	314	135	405	
	3.0	140	140	98	196	84	252	
	2.0	356	356	256	512	222	666	
6.0	2.5	181	181	128	256	110	330	
	3.0	114	114	80	160	68	204	
	2.0	258	258	185	370	161	483	
8.0	2.5	130	130	92	184	79	237	
	3.0	81	81	57	114	49	147	
	2.0	199	199	143	286	124	372	
10.0	2.5	100	100	71	142	61	183	
	3.0	62	62	44	88	37	111	
	2.0	145	145	104	208	91	273	
13.0	2.5	71	71	51	102	44	132	
	3.0	43	43	31	62	27	81	
	2.0	120	120	87	174	76	228	
15.0	2.5	59	59	42	84	36	108	
	3.0	35	35	25	50	22	66	

Notes: Sample size was calculated using the method described by Dupont and Plummer (1990) and specifying an unmatched cohort design: Software implementing this method (PS power and sample size is available at: http://biostat.mc.vanderbilt.edu/wiki/Main/PowerSampleSize

Table 1 shows required number of subjects in voriconazole exposed cohort and other antifungal(s) exposed cohort with different values of the parameters described above. For example, assuming that the rate of p_0 is 5.0% and the voriconazole exposed—to unexposed cohort ratio is 1:2, the study would require at least 157 patients in the voriconazole exposed cohort and 314 patients in the unexposed cohort to detect a rate ratio of 2.5 with 80% power at a 5% significance level.
